2.2.1. Blinding Procedures

The unblinded pharmacist/study team member at the investigational center who will prepare and administer the IMPs will know the IMP assignments for each patient. In addition, during Period 1, up to 2 other unblinded individuals from the investigational center will know the IMP assignments to serve as backup staff or to provide quality assurance and oversight in their preparation and administration, as necessary. These individuals will not be involved in the conduct of any study procedures and assessment of any adverse events and must not discuss any unblinding information with the blinded site staff.

Additional details about the IMP preparation and injection procedure (including measures to mitigate the risk of unblinding) can be found in the pharmacy manual. In order to avoid nonintentional unblinding, the dosing procedure described in the pharmacy manual (including masking measures such as covering the IMP syringe contents, etc) will remain unchanged throughout the study, although after week 8 IMP administration, the treatment in Period 2 allocation will be revealed.

2.2.2. Discontinuation of the Placebo Treatment Group

After approximately 440 patients complete the week 8 visit, depending on the need for additional data on exposure or safety, the placebo treatment group may be discontinued and additional patients may be randomized to the study (ie, to Period 1) to the TV-44749 treatment groups only. Patients randomized to the study from that time point will not be included in the primary efficacy analyses, as there will be no concurrent placebo group. The sponsor will notify the sites and the IDMC once the placebo treatment group is discontinued, and new patients from that time point will sign an updated ICF reflecting the actual available treatment groups.

Once all patients who were still ongoing in Period 1 at the time of the placebo group discontinuation will either complete or early terminate from Period 1, and are randomized into

Period 2 (if applicable), randomization into Period 2 will no longer be performed, as at that point, all patients in Period 1 will be assigned to TV-44749 treatment groups and will continue their treatment assignment in Period 2 as well.

Period 1 will remain blinded until database lock for efficacy, including for patients randomized after the discontinuation of the placebo treatment group as long as they are still in Period 1. After the data are locked for efficacy analyses, the study may continue in an unblinded manner.

Period 1 efficacy data collected from patients randomized after discontinuation of the placebo treatment group will not be included in the primary analysis. Therefore, revealing of Period 1 treatment assignment (ie, since patients will be continuing their treatment assignment in Period 2) for patients who were randomized to the study after discontinuation of the placebo treatment group will not be considered unblinding.

Additional details regarding maintenance of randomization and blinding are described in Section 6.10 of the study protocol.

2.3. Independent Data Monitoring Committee

During the conduct of this study, an Independent Data Monitoring Committee (IDMC) will review accumulated unblinded safety, pharmacokinetic, and efficacy data on a regular basis, as detailed in the IDMC charter, to evaluate the safety of the product for the purpose of ensuring the continuing safety of the study patients and overseeing study conduct issues, as applicable.

The IDMC will be composed of independent physicians with expertise in the relevant therapeutic area and other relevant experts, such as a statistician and a pharmacokinetic expert. The IDMC will receive safety data periodically in an unblinded fashion.

The IDMC chairperson will communicate with the sponsor in regard to issues resulting from the conduct and clinical aspects of the study. The sponsor will work closely with the committee and the unblinded statistician to provide the necessary data for review.

Based on the IDMC interim reviews, the IDMC can make recommendations on study conduct including study termination. After at least 50% of patients who were randomized completed Period 1 PANSS assessment in Week 8 visit, a conditional power estimation may be provided to the IDMC as part of the interim reviews. The conditional probabilities for each of the 3 active treatment groups compared to placebo will be incorporated into the benefit-risk evaluation and decision-making if the IDMC considers study termination. Further details can be found in Section 15.

In addition, the IDMC will review each case of suspected Post injection Delirium/Sedation Syndrome (PDSS) and adjudicate it based on the diagnosis criteria for PDSS, as detailed in the IDMC charter, and agreed upon between the FDA and Teva.

Further details regarding the IDMC roles and responsibilities and the data transfer process are given in the IDMC charter and the unblinded PK analysis plan. Details regarding the analysis and the conditional power approach are described in Section 15.

2.4. Stopping Rules for the Study

During the conduct of the study, all safety data will be reviewed as they are reported from the investigational centers to identify safety concerns.

The study may be terminated by the sponsor for any reason at any time. For example, the sponsor should terminate the study in the event of:

- new toxicological or pharmacological findings or safety issues that invalidate the earlier positive benefit-risk assessment
- discontinuation of the development of the IMP

Based on the IDMC interim reviews, the IDMC can make recommendations on study conduct including study termination. After at least 50% of patients complete Period 1, conditional power may be provided to the IDMC as part of the interim reviews. This information will be incorporated into the benefit-risk evaluation and decision-making by the IDMC, if IDMC considers terminating the study. Further details regarding the conditional power approach can be found in Section 15.

In case the entire study or arms of the study will be stopped, the patients who are terminated early will be followed according to Withdrawal Criteria and Assessments/Procedures for the Patient (Section 5.4 of the study protocol).

2.5. Sample Size and Power Considerations

The following assumptions are made for the sample size determination:

1. Standardized mean difference of [REDACTED]
2. Homogenous variance
3. Overall 2-sided alpha of 0.05
4. Power of [REDACTED]
5. Randomization ratio of 1:1:1:1
6. Truncated Hochberg adjustment for multiplicity

For the sample size calculation, a 2-sample t-test and a [REDACTED] correction (ie, 2-sided alpha of [REDACTED]) were used. A simulation study with the above assumptions was conducted to evaluate the power using mixed-model repeated measures (MMRM) with truncated Hochberg as a multiplicity control method; the power to demonstrate statistically significant superiority in the 3 active treatment groups versus placebo for the primary endpoint was about [REDACTED].

Approximately 440 patients completing week 8 are needed to achieve the above power, per comparison. Despite the fact that missing data after discontinuation will be imputed, for simplicity, it is assumed that the ET rate in Period 1 will be [REDACTED], and the overall sample size is adjusted for that; hence, the number of patients to be randomized is approximately 640.

Once 440 patients complete week 8 in Period 1, randomization to placebo may be stopped, and new patients will then be randomized to the active treatment groups only (Section 2.2.2 above). The efficacy analysis will include all patients randomized until the time point at which

randomization to placebo was stopped. Patients randomized after the randomization to placebo group was stopped will not be included in the efficacy analyses.

2.6. Sequence of Planned Analyses

2.6.1. Planned Interim Analyses

Interim safety and efficacy data will be analyzed and reviewed periodically by an IDMC. Interim analyses will be performed by an unblinded analyses group independent of the sponsor (eg, unblinded statistician). The sponsor will remain blinded to the results of the interim analyses.

Data review meetings will take place according to a set schedule:

- The initial data review meeting will be triggered approximately six months after the first patient is enrolled, when approximately 40 patients will complete two months of treatment in Period 1 of the study. This meeting will include review of data collected during Period 1.
- Thereafter, data review meetings will occur on a quarterly basis and include data collected in Period 1 and Period 2.
- Unscheduled meeting or ad hoc meeting are called by the IDMC chairperson or the CSP or designee when a safety concern arises.
- If a suspected PDSS event occurs, the IDMC will review the case and meet ad-hoc to determine if it fulfills all 5 criteria in the clinical definition of PDSS (further details can be found in the IDMC charter and in the study protocol).

Each meeting is composed of an open session and a closed session (if applicable). In the closed session, unblinded data may be reviewed. Further details are depicted in the IDMC charter.

2.6.2. Final Analyses and Reporting

Final Analysis for efficacy will be performed once approximately 440 patients have completed Period 1, and completed assessment 8 weeks after the first IMP administration of the primary and key secondary efficacy endpoints (PANSS, CGI-S, PSP). At the time for the efficacy database lock, all data available (including safety assessments) from period 1 will be included in the analysis and will be presented. Topline results analysis of the efficacy and safety of period 1 will be conducted according to GSCD-SOP-905 (Top-Line Results Dissemination).

Final Analysis for safety will be performed after the study completion.

This Statistical Analysis Plan and any corresponding amendments will be approved prior to the first database lock, in accordance to GSD-SOP-702 (Statistical Analysis Plan).

The randomization codes for period 1 will be maintained blinded to Teva until this Statistical Analysis Plan has been approved and until the database lock for efficacy analysis will be conducted, in accordance to GSCD-SOP-703 (Release of Blinded Randomization Codes for a Randomized Clinical Study). During the study, the randomization lists (including the patients treatment assignments) will be shared by the Randomization Code Generator vendor with an external unblinded statistician, for the purpose of generating unblinded TLGs for IDMC safety

reviews. The transfer process will be according to the Unblinding Plan (GSCD-SOP-703-FRM02) and will follow all the required steps and instructions described in this plan.

Any change prior to unblinding along with the reasons for the change will be described in the statistical analysis plan. After unblinding of Period 1, any additional analyses or changes to analyses that may be required will be fully disclosed in the clinical study report (CSR). In the event of any contradiction between the study protocol and the statistical analysis plan, the statistical analysis plan will prevail.

3. ANALYSIS SETS

3.1. Full Analysis Set

The full analysis set will include all patients randomized to Period 1 regardless of the actual treatment the patients received.

The treatment assignment for this analysis set will be according to the randomization assignment in the opening of each Period (Visit 2 for Period 1 and Visit 11 for Period 2).

This analysis set will be used for selected exploratory efficacy analyses and supplementary analyses, unless otherwise specified.

3.2. Efficacy Analysis Set

The efficacy analysis set will include all patients randomized to Period 1 while patients are randomized to either one of the three TV-44749 doses or placebo, regardless of the treatment the patients actually received. As. The efficacy analysis set will not include patients randomized to Period 1 after the randomization to placebo group was stopped (Section [2.2.2](#)).

This analysis set will be used for the primary efficacy estimand and other efficacy type-I error controlled endpoints analyses specified below.

3.3. Safety Analysis Set

The safety analysis set for Period 1 will include all randomized patients who received at least 1 dose of TV-44749 or placebo. The safety analysis set for Period 2 will include all randomized patients to Period 2 who received at least 1 dose of TV-44749. For the integrated study periods summary tables (see Section [8](#)) the safety analysis set will include all patients in the safety analysis set of period 1 that received 1 of the 3 TV-44749 treatments groups, or all patients that meet the definition of the safety analysis set of Period 2.

In each of the safety analysis sets, treatment will be assigned based on the initial treatment patients actually received in the corresponding period, regardless of the treatment to which they were randomized, and regardless of dose adjustments, unless otherwise specified. For the integrated periods summary tables, patients randomized in Period 1 to 1 of the 3 TV-44749 groups will be counted according to the initial dose they actually received in Period 1. Patients that were randomized to Placebo in Period 1 will be counted according to the initial dose of TV-44749 they actually received after the re-randomization of those patients to the 1 of the 3 TV-44749 treatment groups in Period 2, regardless of dose adjustment that may occur during Period 2.

In cases of dosing error, a decision of what is the treatment assignment for these patients will be made in a blinded manner prior to unblinding of Period 1, as applicable. The decision will be made during the statistical data review meeting and will be documented in the statistical data review document.

For IDMC monitoring during the study, the safety analysis set will use the treatment based on the randomization assignment in the opening of each period.

3.4. Pharmacokinetic Analysis Set

The pharmacokinetic analysis set will include those patients from the safety analysis set of the integrated study periods (see Section 4.1) who received at least one dose of TV44749 and have ≥ 1 Olanzapine plasma concentration value available.

4. GENERAL ISSUES FOR DATA ANALYSIS

4.1. General

Descriptive statistics for continuous variables include n, mean, standard deviation (SD), median, minimum, and maximum. When appropriate, least squares means and standard errors (SE) are presented. Descriptive statistics for categorical variables include patient counts and percentages. Missing categories will be displayed as appropriate.

For the CSR and IDMC closed reports, summary tables by treatment groups will have 2 versions – (a) summary tables for Period 1; (b) summary tables for the integrated periods including patients from both Periods (Period 1 & Period 2), unless otherwise specified. For IDMC open reports, a summary tables for Period 1 and Period 2 will be generated and will only be presented overall (total).

4.2. Specification of Baseline Values

For Period 1, the baseline value for a patient is the last observed data that was collected for this patient prior to the first IMP dose administration, unless otherwise noted.

For Period 2, the baseline value for a patient is the last observed data that was collected for a patient prior to the third IMP administration (i.e., first administration in period 2, at visit 11, week 8), unless otherwise specified (see procedures and assessments which may be performed after the re-randomization to Period 2 at visit 11 in Section 6.9.1 in the study protocol).

For the integrated periods to be presented in the CSR and during the IDMC closed (in an unblinded manner) and open (in a blinded manner) sessions, the baseline values of patients initially randomized in Period 1 to TV-44749 groups will be defined as the last observed data that was collected prior to the first TV-44749 dose administration. For patients that were assigned to placebo group in Period 1, the baseline value is the baseline value for Period 2 (see above paragraph).

It should be noted that the baseline values of placebo patients will differ between tables presented in the integrated periods summaries and those presented in Period 1 summaries.

4.3. Handling Withdrawals and Missing Data

Despite the best efforts to obtain complete data, missing data is unavoidable. Unless otherwise specified, only observed patient data will be used in the statistical analyses.

According to the definition of the primary efficacy estimand, it is planned to assign multiple possible values to each missing efficacy data point (i.e., missing primary and secondary efficacy endpoints) by employing multiple imputation methodology (see Section 4.3.1 and Section 6.2.2), in addition a multiple imputation procedure is planned to assess the robustness of the underlying assumption for the primary efficacy analysis using the tipping point approach (see Section 17 and [Appendix A](#) below).

Ad-hoc imputation for safety summary tables will be performed only for the specific cases described below. There will be no imputation in the data listings (including ad-hoc imputation); all values will be displayed as recorded in the clinical database. No imputation will be performed for missing items in efficacy and safety scales.

4.3.1. Imputation for Primary Efficacy Analysis

[REDACTED]

[REDACTED]

[REDACTED]

4.3.2. Ad-hoc Imputation for Safety Data

[REDACTED]

[REDACTED]

[REDACTED]

[REDACTED]

[REDACTED]

4.3.3. Missing items in the Quality of Life Questionnaires

[REDACTED]

[REDACTED]

[REDACTED]

[REDACTED]

4.3.4. Handling of Adverse Events with Missing Dates

For the purpose of this study, oral olanzapine is not considered an IMP. Any adverse event with incomplete start dates will be handled as described below, and end dates will not be imputed.

- If only the start day of an adverse event (but not the month) is missing, then the start day will be imputed as the first day (01) of the month, unless otherwise specified. If the adverse event month is not missing and it is the same month as that of randomization, the start date will be imputed as the first IMP administration date during that month.
- If both the day and month are missing and the year is the year of the date of first study treatment then the date will be imputed as the date of first IMP administration, unless the adverse event end date occurred prior to the date of first study treatment, in which case the start day-month will not be imputed. In addition, if the date of first IMP administration year is < the year of the adverse event start year then the start day-month will be imputed as 01 and January, respectively.

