After approximately 440 patients complete the week 8 visit, depending on the need for additional data on exposure or safety, the placebo treatment group may be discontinued and additional patients may be randomized to the study (ie, to Period 1) to the TV-44749 active treatment groups only. For further details, see Section [2.2.2 Discontinuation of the Placebo Treatment Group](#).

During the conduct of this study, an Independent Data Monitoring Committee (IDMC) will review accumulated unblinded safety, pharmacokinetic, and efficacy data on a regular basis, as detailed in the IDMC charter, to evaluate the safety of the product for the purpose of ensuring the continuing safety of the study patients and overseeing study conduct issues, as applicable. The IDMC will not evaluate efficacy for early efficacy or early futility.

Once all patients completed Period 1, and Period 2 is ongoing, an analysis of the full efficacy data will be performed.

Screening (up to 8 days Prior to Randomization to Period 1):

Patients will undergo screening procedures and assessments up to 8 days prior to randomization to Period 1. Patients will provide informed consent at the screening visit before any study-related procedures are performed. Patients will be asked to consent to share their information with a vendor that will verify that they are not currently participating or have not recently participated in another clinical study, unless prohibited by local requirements. [REDACTED]

[REDACTED]

[REDACTED]

[REDACTED]

[REDACTED]

[REDACTED]

Patients with exacerbation that started \leq 8 weeks prior to screening (the investigator should confirm the exacerbation based on the patient's medical records and/or based on anamnesis) and who would benefit from psychiatric hospitalization or continued hospitalization for symptoms of schizophrenia may be included in this study.

The patient's total Positive and Negative Syndrome Scale (PANSS) score should be between 80 and 120, inclusive, at screening with a score \geq 4 on at least 2 of the following 4 items of the PANSS positive sub-scale: hallucinatory behavior, delusions, conceptual disorganization, or suspiciousness/persecution.

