8.4. Adverse Events

Adverse events will be collected and recorded from the time a patient signs the informed consent to the end of follow-up period.

All adverse events will be coded using the Medical Dictionary for Regulatory Activities (MedDRA version 26.0 or later). Unless otherwise specified, adverse events will be summarized by SOC and preferred term, with preferred terms within SOCs presented in descending order of patient incidence. Multiple records with the same PT or SOC category and adverse event onset date for the same patient, or with overlapping or consecutive dates, are counted only once for the adverse event with the highest severity and seriousness.

Adverse events summaries will be presented for Period 1 separately and for the integrated study periods separately. Adverse events that started in Period 1 and ended in Period 2 will be reported only in Period 1, and will be presented only once in the integrated summary table.

Summaries will include treatment-emergent adverse events that are defined as adverse events that occurred at or after the first IMP injection was administered through the end of the treatment (including the assessment collected in the End-of-Treatment/ Early Termination visit).

Additional summaries will be presented for the follow-up period (after the End of Treatment/Early Termination visit and until the end of the study).

Summaries will be presented for all adverse events (overall and by severity), including adverse events defined by the investigator as related or with missing relationship to IMP treatment and/or device (overall and by severity), serious adverse events, serious adverse device events and adverse events and adverse device events causing withdrawal from the study and withdrawal from the treatment. All summaries will be presented by treatment group and overall (total), using exposure categories.

Protocol defined adverse event of special interest (PDAESI) (section 8.1.7 of the study protocol) will also be summarized and presented by treatment group and by visit..

The summary tables for adverse events will be presented by the treatment group to which the patient were assigned according to the safety analysis set. A separate summary tables will be presented, excluding the patients with at least one dose adjustment. Additional analysis may be initiated if the results of those summaries will judged by the study team to be significantly different.

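### SAP 4.3.4 dates a day-missing adverse event in the month of randomization to the first injection without checking its end date, so an event recorded as over before dosing counts as treatment-emergent

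*SAP*

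**What the plan says.** SAP Section 4.3.4 opens with two general statements: "For the purpose of this study, oral olanzapine is not considered an IMP", and "Any adverse event with incomplete start dates will be handled as described below, and end dates will not be imputed". Two bullets follow.

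- **First bullet, only the start day missing.** The default is that "then the start day will be imputed as the first day (01) of the month, unless otherwise specified". A special case follows: when the month is known and "it is the same month as that of randomization, the start date will be imputed as the first IMP administration date during that month". No condition on the end date is attached to either sentence.
- **Second bullet, day and month both missing, year equal to the year of first treatment.** The start is set to the day of the first injection, "unless the adverse event end date occurred prior to the date of first study treatment, in which case the start day-month will not be imputed".

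SAP Section 8.4 sets the collection window: "Adverse events will be collected and recorded from the time a patient signs the informed consent to the end of follow-up period". Its summaries cover "treatment-emergent adverse events that are defined as adverse events that occurred at or after the first IMP injection was administered". The same section sends missing adverse event dates to Section 4.3 for imputation. Section 4.3 adds that nothing is imputed in the data listings.

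**The concern.** Because events are collected from consent, the database will hold events from screening. In that window patients taper their previous oral antipsychotics. Those without olanzapine in the past year also take two daily oral doses to test tolerability (Protocol Section 4.1). The SAP treats oral olanzapine as outside the IMP, so an event that arose and resolved on it is pre-treatment.

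The first bullet can reverse this. If the site knows when the event ended but not the day it began, the start is moved to the injection even though the recorded end proves that the event was over by then. There is no doubt left for a conservative rule to resolve. The second bullet shows that the authors saw the problem for the vaguer date and left the more informative one unguarded.

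At stake is the accuracy of the treatment-emergent counts, and their agreement with listings that would show the same event ending before dosing. In the integrated tables, SAP Section 8.1 drops Period 1 data from placebo patients, so any such event there would come only from patients randomized to TV-44749 in Period 1. Efficacy is not involved.

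**Working it through.** The plan gives no figure to reproduce. The check is to apply the rule as written to test dates, then apply it again with the second bullet's exception added.

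**Inputs.** The imputation rules and the statement that end dates are not imputed come from SAP 4.3.4. The treatment-emergent definition comes from SAP 8.4. The screening length comes from SAP 2.1: "Patients will undergo screening procedures and assessments up to 8 days prior to randomization to Period 1", with a permitted extension to day 10. The calendar dates below are assumed for illustration: randomization and first injection on 15 March, onset in March with the day missing.

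**Step 1. Apply the rule.** The month matches that of randomization, so the start is 15 March whatever the end date. An event is treatment-emergent if its start is on or after 15 March.

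| Recorded end | Start as written | Treatment-emergent as written | Start minus end | Start with the exception added |
|---|---|---|---|---|
| 10 March | 15 March | yes | 15 − 10 = 5 days | not imputed |
| 14 March | 15 March | yes | 15 − 14 = 1 day | not imputed |
| 17 March | 15 March | yes | 15 − 17 = −2 days | 15 March |

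The first two rows are wrong as written: the start falls after the end, and a pre-dose event is counted. The third row is the usual conservative choice for an event that could have begun either side of the dose. The exception leaves it unchanged.

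**Step 2. Locate the fault.** Under the first-of-month default, the start would be 1 March, before the injection, and the event would not count. An event whose start month precedes the month of randomization gets the first of that earlier month and is also handled correctly. Only the special case for the month of randomization produces the error.

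**Step 3. How much of screening the special case covers.** Assume first injections are spread evenly over the calendar, with an average month of 30.44 days. A day k days before the injection then falls in the same month with probability of about 1 − k/30.44.

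- 8-day window: the mean of k is 4.5, so 1 − 4.5/30.44 = 0.85.
- 10-day window: the mean of k is 5.5, so 1 − 5.5/30.44 = 0.82.

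These are shares of screening days that lie in the month of the first injection. They show that the special case is not a calendar rarity. They do not estimate how many events are misclassified, because the start day must also be missing and a pre-injection end must be on record. The documents give no basis for either frequency.

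**The case against.** The strongest reply is that the triggering record will seldom occur. Patients are hospitalized throughout screening. Adverse events are asked about at screening and at baseline (Protocol Table 1). Onset and end dates must be recorded (Protocol Section 8.1.2), and missing data are queried with the site (Protocol Appendix J). A site would have to know the end of an event but not its start day within about a week of inpatient observation. This stands and limits the size of the point.

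It can also be said that dating an uncertain event to first dose is a normal conservative convention, and that SAP Section 4.3.2, on ad-hoc imputation for safety data, is redacted and might hold a general consistency rule. The first is right for events that were ongoing or ended on or after the injection date, but not for an event whose end is recorded as earlier. The second cannot be excluded. Still, 4.3.4 is the section specific to adverse event dates, and its visible text states the exception for one case only.

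A reader might infer more than the documents support:

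- **That about 85% of day-missing screening events are misclassified.** That figure is the calendar share from Step 3, and only events with a recorded pre-injection end are wrong.
- **That negative durations distort the analysis.** A derived start can fall after the end, but SAP 8.4 plans no summary of event duration, and listings keep the recorded values.
- **That the comparison with placebo is biased.** The events arise before the first injection and the rule is the same in all four Period 1 arms, so no systematic difference is expected in the Period 1 tables.
- **That oral olanzapine effects will appear as first-injection effects.** This could happen in a single record; nothing in the documents shows that it will happen often.

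**Conclusion.** The special case in the first bullet of SAP 4.3.4 is wrong as written. For an event that meets all three conditions (missing start day, start month equal to the month of randomization, recorded end before the first injection), it yields a start after the end and a treatment-emergent classification that the record contradicts.

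The size is small and cannot be quantified from the documents. The expected effect is a slight inflation of absolute treatment-emergent counts in descriptive tables. The conclusion assumes that 4.3.4 governs adverse event dates as printed and that the redacted 4.3.2 does not override it.

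**What to change.** Extend the second bullet's end-date exception to the special case in the first bullet. If the recorded end date precedes the first IMP administration, the start is not moved to the injection date and the event is classified as not treatment-emergent. State the classification explicitly, because an event left without an imputed start has no complete date to compare with the injection. Keep first-dose imputation for events that were ongoing or that ended on or after the injection date.

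The cost is one sentence in the SAP and one condition in the program that derives adverse event dates. No data collection changes. If Section 4.3.2 already contains such a rule, a cross-reference in 4.3.4 is enough.
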